Basic demographic data (BMI, gender, race, education, income, household size), physical activity data (IPAQ long), and eating behavior questions (TFEQ) and 2 questions measuring delayed gratification will be collected upon enrollment. We will also collect this data, minus the demographic questions, at 6 and 12 months.

Protocol

Abstract

Obesity is the second leading cause of preventable death in the United States, (1) associated with high blood pressure (BP), type 2 diabetes, coronary heart disease, and osteoarthritis. Identifying effective strategies for treating obesity is both a clinical challenge and a public health priority. Over 70% of the U.S. population is overweight or obese, and obesity in middle age translates into higher rates of hospitalization, Medicare expenditures, disability, and mortality risk in subsequent years. While a variety of approaches are successful in achieving initial weight loss, techniques for maintenance of initial weight loss have largely been unsuccessful.

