Our previous work examining the impact of different degrees of cost sharing on employee participation, engagement, and ongoing weight loss showed that among Weight Watchers members who had initial success in losing at least 5% of their initial body weight, the majority regained weight over the subsequent 6 months; Weight Watchers members in general were at high risk of dropping out of the program altogether perhaps due to lack of success in losing weight and keeping it off (John et al 2015). Research has shown that the frequency of self-weighing is important for both prevention of weight gain and weight loss (Wing et al NEJM 2006; 355:1563-1571; Linde JA et al Ann Behav Med 2005; 30: 210-216). This study will build on our successful efforts using incentives for weight loss to test scalable ways of increasing the frequency of self-weighing among Weight Watchers members who had initial success in losing weight. This 2- arm randomized controlled trial will compare the relative effectiveness and cost-effectiveness of (1) weekly feedback without incentives to (2) weekly escalating lottery-based incentives among patients who successfully lost at least 5 kg over 4-6 months during participation in Weight Watchers (Pre Phase). Incentives will be provided to some study participants (Arm 2) for the first 6 months (Phase I), and then participants will be followed for 6 more months to examine effects following cessation of incentives (Phase II). A total of 259 participants will be randomized into the 2 arms.

Specific Aims

Aim 1: Among participants who lose 5 kg or more of baseline weight prior to randomization, assess the effectiveness of escalating lottery rewards, relative to the control group, on maintenance of weight loss over the ensuing 6 months (Phase I).

Aim 2: Assess the degree to which weight loss is maintained in the intervention group relative to usual care during the 6 months following the cessation of the interventions (Phase II).

Objectives

Overall objectives

- 1. Among participants who lose 5 kg or more of baseline weight prior to randomization, assess the effectiveness of escalating lottery rewards, relative to the control group, on maintenance of weight loss.
- 2: Assess the degree to which weight loss is maintained in the intervention groups relative to usual care during the 6 months following the cessation of the interventions (Phase II).

Primary outcome variable

Pounds of weight lost at the end of 6 months

Secondary outcome variables

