To enhance retention, we will provide a total of \$100 to participants in all arms. Participant compensation will be independent of degree of weight loss and randomization group as follows: \$50 for completing an online survey at the end of month 6 and at the end of month 12. All participants will also receive a free scale (value \$179). All payments will be approved electronically from the Way to Health platform. Payment information will be sent to Wells Fargo to process and sent to participants via check. Participants will receive an automated message from the Way to health platform notifying them of compensation after completing each required survey. Participants in the financial incentive arm of the study will receive additional payments based on their adherence to daily weighing at home as outlined below in Study Procedures.

Statistical Methods

Sample size justification

We have designed the study with adequate power to detect differences in maintenance of initial weight loss. Our intervention should achieve its maximal impact in maintaining initial weight loss at the end of Phase I, when the incentive payments cease. The primary analysis will be an intent-to-treat analysis that compares the weight loss at 6 months between the lottery and control arms, using a t-test at the 0.05 level for significance. Assuming 20% missingness, a 5 kg (11 lb) SD for weight change at 6 months, and at least 5 lb more weight loss for the intervention arm compared to control at 6 months, we will have at least 90% power to detect the improvement in our primary outcome.

Analytic approach

Primary and key secondary outcomes

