The primary analysis will be an unadjusted between-arm comparison of the change in weight from baseline (randomization) to 6 months, using a t- test performed at the 0.05 significance level. The primary analysis will be done as an intent-to-treat (ITT) analysis, including each participant in the group to which she was randomized, regardless of adherence to the assigned intervention. The 6-month weight is determined as the first weight that is inside the 6-month visit window. A multiple imputation strategy based on baseline covariates (including study arm) will be used to fill in the missing data for the primary outcome. For more details see multiple imputation strategy below. A complete case analysis will be done as a sensitivity analysis. A second sensitivity, assuming weight returned to baseline (weight at time of randomization) may also be considered. We will also estimate the difference between arms at 6-month in an adjusted analysis where the change from baseline is regressed in a linear model on study arm, baseline weight, and other covariates including age, sex, race, BMI, education, income, and physical activity (total MET-minutes/week).

Analyses of the key secondary outcome, weight change between baseline and 12 months (Phase 2) will be conducted in a similar manner as the primary outcome. The 12-month weight is determined as the weight that is the first weight inside the 12-month visit window. The multiple imputation algorithm for the 12-month outcome will additionally consider the 6-month weight outcome as an additional predictor, using a chained imputation type approach.

Multiple Imputation Strategy

Missing primary outcome data, weight at 6 months, will be imputed using baseline covariates only (Imputation A); variables include age, sex, race, weight, BMI qualifying weight loss, education, income, IPAQ activity level, MET-minutes walking, the three domains of eating behaviors (cognitive restraint, uncontrolled eating, emotional eating, and two scores related to delayed gratification behavior. A supportive analysis will also be done also using post-randomization variables (Imputation B); these variables include the most recent logged weight and time since last weight, The imputation strategy for the weight at 12 months and other secondary outcomes will proceed in a similar manner. Weight at 12 months will additionally use the 6-month weight outcome, using chained imputation approach (1).

Analysis of other outcomes

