The trend over time for the frequency of at-home weight measurements will be compared between arms using a generalized estimating equation (GEE) with an autoregressive (AR-1) working correlation model; specifically the mean number of days out of 7 is modeled and compared among study arms adjusting for study week and a week-by-arm interaction. Separate models will be fit for Phases 1 and 2. A linear mixed effects model with random intercept and slope for week will also be considered. An overall average weekly frequency of weighing in will be compared between arms for Phase I and Phase II using a similar GEE approach.

Additional secondary analyses include a between-arm comparison of the percent of individuals who maintained their weight (defined as gaining no more than 1.36 kg or 3 lbs) at 6 and 12 months. We will consider whether the amount of weight gain is correlated with the average number of times per week participants weighed themselves in a cross-sectional analysis at 6 and 12 months. Comparisons will also be made of the changes in self-reported physical activity and the three domains of eating behaviors (cognitive restraint, uncontrolled eating, emotional eating) at 6 months and 12 months after initial weight loss. Descriptive analyses will be done to examine the proportion of the time people fall off the lottery escalation ladder and the number of resets to beginning for the lottery incentive arm. All secondary analyses will follow in a manner similar to the primary analysis, considering both an unadjusted and adjusted approach. Imputation models for the secondary outcomes will include as predictors the baseline value for that outcome and the other baseline covariates considered for the imputation strategy A model, as described above. For secondary outcomes with < 10% data missing data, only a single imputation strategy (imputation A) may be considered.

Exploratory Analyses

We will summarize the frequency of the self-reported weights in Phase I and Phase II and examine whether there will be a difference by arm. We will further explore intervention effects and examine whether there may be a potential interaction between the baseline delayed gratification score and treatment arm.

Study Procedures

Procedures

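### Neither imputation strategy names the 6-month survey score as a predictor of missing 12-month activity and eating scores, although 6-month weight is used for 12-month weight

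*Combined protocol and SAP*

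**What the plan says.** Secondary outcomes 8 and 10 are self-reported physical activity and eating behavior at 12 months. Both surveys are given at enrollment and again later. The section Administration of Surveys and/or Process says: "We will also collect this data, minus the demographic questions, at 6 and 12 months". A 6-month score will therefore often exist for someone whose 12-month score is missing.

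Three statements govern the imputation:

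- Analysis of other outcomes gives the predictors: "Imputation models for the secondary outcomes will include as predictors the baseline value for that outcome and the other baseline covariates" used in Imputation A. No 6-month score is named.
- Multiple Imputation Strategy treats weight differently: "Weight at 12 months will additionally use the 6-month weight outcome, using chained imputation approach". The section Primary and key secondary outcomes says the same, again for weight alone.
- Multiple Imputation Strategy also sets up a supportive Imputation B with post-randomization variables. Those it names are the last weight recorded and how long ago it was recorded. It says that the other secondary outcomes will be handled along similar lines. Analysis of other outcomes then allows Imputation A to stand alone when under 10% of an outcome is missing.

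**The concern.** Take a participant who completes the month-6 survey and skips the month-12 survey. Under the listed predictors, the missing score is filled in from baseline data, and the month-6 answer plays no part. If skipping month 12 depends on the 6-month score, the data are missing at random given that score but not given baseline alone. Where that dependence differs between arms, the 12-month contrast is biased. Some precision is lost in any case.

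A difference between arms is conceivable here, because the lottery arm loses its weekly lottery at month 6 and the control arm has none to lose. This is an inference from the design; the documents do not report it. At stake are the 12-month survey contrasts, which help to show what happens to behavior once incentives stop.

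**Working it through.** **The plan's own figure.** The only stated power is for 6-month weight change, and this point does not touch it. Inputs from Sample size justification: "using a t-test at the 0.05 level for significance" (two-sided assumed); "Assuming 20% missingness, a 5 kg (11 lb) SD for weight change at 6 months"; "at least 5 lb more weight loss for the intervention arm compared to control at 6 months". The abstract gives the total of 259, randomized 1:1.

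- Evaluable per arm: 259/2 × 0.8 = 103.6.
- Standard error: 11 × √(2/103.6) = 1.528 lb, and 5/1.528 = 3.27.
- Power: Φ(3.27 − 1.96) = 90.5%, or 90.3% with the noncentral t. This agrees with "we will have at least 90% power to detect the improvement in our primary outcome".
- At 90% power, 204 evaluable participants are needed, and 204/0.8 = 255, against 259 planned.

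**Inputs for the survey outcomes.** The documents give no correlation, missing share or drop-out pattern for these scores, so all of the following are assumed: equal correlation r of 0.5 or 0.7 among the baseline, 6-month and 12-month scores; 10 to 30% missing at month 12; every 6-month score observed.

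**Variance explained.** With baseline alone, R² = r². With baseline and the 6-month score, R² = 2r²/(1 + r).

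- r = 0.5: 0.25 rises to 0.50/1.5 = 0.33.
- r = 0.7: 0.49 rises to 0.98/1.7 = 0.58.

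**Precision, missing completely at random.** With missing fraction m and many imputations, the variance of an arm mean relative to complete data is 1 + [m/(1 − m)](1 − R²).

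- m = 0.1, r = 0.5: 1.0833 against 1.0741; the interval narrows by 1 − √(1.0741/1.0833) = 0.4%.
- m = 0.3, r = 0.7: 1.2186 against 1.1815; it narrows by 1.5%.
- m = 0.2 gives 0.9% (r = 0.5) and 1.0% (r = 0.7).

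**Bias when drop-out depends on the 6-month score.** This is a simulation of one million participants per setting, with a true effect of 0.3 SD at months 6 and 12, 20% missing overall, and lower 6-month scores more likely to be missing (log-odds slope 0.8 per SD). Regression imputation was run with and without the 6-month score. Bias is the estimate minus the full-data contrast, in SD.

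| r | Arm(s) where drop-out depends on the score | Baseline only | With 6-month score |
|---|---|---|---|
| 0.5 | Control only | −0.040 | −0.002 |
| 0.5 | Lottery only | +0.037 | +0.001 |
| 0.5 | Both | −0.006 | 0.000 |
| 0.7 | Control only | −0.033 | 0.000 |
| 0.7 | Lottery only | +0.029 | −0.002 |
| 0.7 | Both | −0.005 | +0.001 |

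**Scale.** With 103.6 observed per arm, the standard error of a raw contrast is √(2/103.6) = 0.139 SD. A bias of 0.03 to 0.04 SD is thus 0.22 to 0.29 standard errors. If a bias of that size arose with no true effect, a nominal 5% two-sided test would reject about 5.5 to 6.0% of the time: Φ(−1.96 + 0.22) + Φ(−1.96 − 0.22) at the lower end, and the same with 0.29 at the upper.

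**The case against.** A reader might infer that the plan has decided to impute these outcomes from baseline alone and to discard the 6-month answer. The text does not go that far, for three reasons. The predictor sentence says what the models will include, which is not an exclusive list; the explicit restriction to baseline covariates is written for Imputation A of 6-month weight. Imputation B, with post-randomization variables, appears to extend to other secondary outcomes, because Imputation A alone is allowed only below 10% missing. And B's named variables are introduced as inclusions, the first being the latest value of weight itself. Carried over to a survey, that could mean the latest survey score. All of this stands, so the defect is an omission that leaves the model open, and not a stated choice. It does not remove the point: B is only supportive, it may be skipped below 10% missing, and it still names no survey score.

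Nor does the extra detail for weight show that the survey outcomes were deliberately treated as inferior. The plan calls 12-month weight change its key secondary outcome, and fuller specification there is ordinary.

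The remaining objection is size. The larger bias needs drop-out to depend on the score in one arm only; with the same dependence in both arms it nearly vanishes. The gain is confined to people with a month-6 survey and no month-12 survey, and each survey is paid $50, which may keep that group small. This also stands, and it limits the point to a minor improvement.

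**Conclusion.** The point holds in limited form. No imputation model in the plan names the 6-month activity or eating score for the matching 12-month outcome, although the score is collected and the parallel step is specified for weight.

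Under the assumptions above, the omission costs about 0.03 to 0.04 SD of bias with one-arm dependence, about 0.005 SD with equal dependence, and 0.4 to 1.5% of interval width. These figures describe a baseline-only model in which every 6-month score is available, so they overstate the cost if 6-month scores are often missing too or if Imputation B would use them. A steeper one-arm mechanism gives more: 0.073 SD in a simulation of trials of 260 with about 25% missing at month 12, a 6- to 12-month correlation of 0.7 and a log-odds slope of 1.0. Nothing in the documents points to that setting.

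It would be wrong to infer that the main result is at risk. Only secondary outcomes are affected.

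**What to change.** In Analysis of other outcomes, after the sentence on predictors for secondary outcomes, add: 'Imputation of 12-month activity and eating outcomes also uses the 6-month value of the same outcome, in the same chained approach as for 12-month weight.'

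The cost is one sentence. The 6-month surveys are already collected, and chained imputation is already planned for weight, so no new data, participants or methods are needed. The sentence also settles how the supportive strategy should be read for these outcomes.
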